6.2.3 Laboratory Procedures/Assessments

Details regarding specific laboratory procedures/assessments to be performed in this trial are provided below Laboratory Safety Evaluations (Complete Blood Count, Comprehensive Serum Chemistry Panel and Urinalysis)

Laboratory tests for complete Blood Count, comprehensive serum chemistry Panelurinalysis, and others are specified in Table 6.

Product: Pembrolizumab and Lenalidomide
Protocol/Amendment No.: Version 3.1 July 18th, 2017

Table 6 Laboratory Tests

Hematology	Chemistry	Urinalysis	Other
Hematocrit	Albumin	Blood	Serum β -human chorionic gonadotropin [†]
Hemoglobin	Alkaline phosphatase	Glucose	(β -hCG) [†]
Platelet count	Alanine aminotransferase (ALT)	Protein	PT (INR)
WBC (total and differential)	Aspartate aminotransferase (AST)	Specific gravity	aPTT
Red Blood Cell Count	Lactate dehydrogenase (LDH)	Microscopic exam (If abnormal)	Total triiodothyronine (T3)
Absolute Neutrophil Count	Carbon Dioxide ‡	results are noted	Free tyroxine (T4)
Absolute Lymphocyte Count	(CO₂ or biocarbonate)	Urine pregnancy test †	Thyroid stimulating hormone (TSH)
	Uric Acid		
	Calcium		
	Chloride		Blood for correlative studies
	Glucose		
	Phosphorus		
	Potassium		
	Sodium		
	Magnesium		

Product: Pembrolizumab and Lenalidomide

Protocol/Amendment No.: Version 3.1 July 18th, 2017

Hematology	Chemistry	Urinalysis	Other
	Total Bilirubin		
	Direct Bilirubin (If total bilirubin is elevated above the upper limit of normal)		
	Total protein		
	Blood Urea Nitrogen		

† Perform on women of childbearing potential only. If urine pregnancy results cannot be confirmed as negative, a serum pregnancy test will be required.
 
‡ If considered standard of care in your region.
			

Product: Pembrolizumab and Lenalidomide
Protocol/Amendment No.: Version 3.1 July 18th, 2017

Laboratory tests for screening or entry into the Second Course Phase should be performed within 10 days prior to the first dose of treatment. After Cycle 1, pre-dose laboratory procedures can be conducted up to 72 hours prior to dosing. Results must be reviewed by the investigator or qualified designee and found to be acceptable prior to each dose of trial treatment.

6.2.3.1 Pharmacokinetic/Pharmacodynamic Evaluations

6.2.3.1.1 Blood Collection for Serum Pembrolizumab

Sample collection, storage and shipment instructions for peripheral blood samples will be provided in the Laboratory Manual.

6.2.3.1.2 Blood Collection for Anti-Pembrolizumab Antibodies

Sample collection, storage and shipment instructions for peripheral blood samples will be provided in the Laboratory Manual.

6.2.3.2 Withdrawal/Discontinuation

When a subject discontinues/withdraws prior to trial completion, all applicable activities scheduled for the final trial visit should be performed at the time of discontinuation. Any adverse events which are present at the time of discontinuation/withdrawal should be followed in accordance with the safety requirements outlined in Section 7.2 - Assessing and Recording Adverse Events. Subjects who a) attain a CR or b) complete 24 months of treatment with pembrolizumab may discontinue treatment with the option of restarting treatment if they meet the criteria specified in Section 7.1.5.5. After discontinuing treatment following assessment of CR, these subjects should return to the site for a Safety Follow-up Visit (described in Section 7.1.5.3.1) and then proceed to the Follow-Up Period of the study (described in Section 7.1.5.4).

6.2.4 Visit Requirements

Visit requirements are outlined in Section 6.0 - Trial Flow Chart. Specific procedure-related details are provided above in Section 7.1 - Trial Procedures.

6.2.4.1 Screening

6.2.4.1.1 Screening Period

The screening phase is the interval between the signing of the Informed Consent Form (IFC) and the day the subject is enrolled in the study (cycle 1 day 1). Informed consent must be obtained prior to performing any study-specific procedures. Assessments that are required to

Product: Pembrolizumab and Lenalidomide
Protocol/Amendment No.: Version 3.1 July 18th, 2017

demonstrate eligibility may be performed over 1 or more days during this phase. The maximum screening period is 30 days.

Results from the screening visit evaluations will be reviewed to confirm subject eligibility prior to enrollment/administration of study drug(s). Tests with results that fail eligibility requirements may be repeated once during the screening phase, if the Investigator believes the results to be in error or not representative. Additionally, a subject who fails screening may repeat the screening process 1 time, if the Investigator believes there has been a change in eligibility status (e.g. following recovery from an infection).

Additionally the screening period will be utilized to determine the baseline assessments of clinical condition and disease status. Tumor assessments appropriate to the type of malignancy will be performed and recorded in CRF.

6.2.4.2 Treatment Period

One therapy cycle is 21 days, treatment will continue until disease progression or toxicity up to 12 months

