1.0 TRIAL SUMMARY

Abbreviated Title	Pembrolizumab and lenalidomide in Patients with Relapsed Refractory Non-Hodgkin and Hodgkin Lymphoma (HL)
Trial Phase	Phase I/II
Clinical Indication	Phase 1: Relapsed B cell HL and non-Hodgkin lymphoma (NHL); Phase 2: relapsed refractory (RR) HL
Trial Type	Therapeutic intervention
Type of control	n/a
Route of administration	Pembrolizumab IV; Lenalidomide PO
Trial Blinding	n/a
Treatment Groups	Phase 1: 9 patients expected (12 patients if unexpected toxicity) with relapsed HL and NHL Phase 2: 17 patients with RR HL
Number of trial subjects	26 (up to 29 if unexpected toxicity)
Estimated enrollment period	18-24 months
Estimated duration of trial	36-48 months
Duration of Participation	Until disease progression or toxicity up to 2 years

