2.0 TRIAL DESIGN

2.1 Trial Design

This is a Phase 1/2 open label study of the combination of pembrolizumab and lenalidomide and in patients with relapsed/refractory (RR) non-Hodgkin lymphoma (NHL) and Hodgkin lymphoma (HL).

Dose escalation will follow a standard 3+3 design. Patients will be treated in cohorts of 3 patients starting with Dose Cohort A with lenalidomide 15mg PO day 1-14 and pembrolizumab 200mg IV day 1, in cycles of 21 days, until disease progression or toxicity up to 24 months. The number of patients expected to be enrolled in the dose escalation study is 9 (up to 12 patients if unexpected toxicity is observed).

If 0 out of 3 patients at a particular dose level experiences a dose limiting toxicity (DLT) within Cycle 1 of treatment, if in Dose Cohort A (lenalidomide 15mg) dose escalation will proceed to cohort B (lenalidomide 20mg), if in Dose Cohort B, 3 additional patients will be added. If a DLT occurs in 0 of 6 patients enrolled on Dose Cohort B this will be deemed the Maximum Tolerated Dose (MTD).

If a DLT occurs in only 1 out of 6 patients enrolled at a particular dose level, dose escalation will occur, however, if this occurs on Dose Cohort B (lenalidomide 20 mg) or Dose Cohort Z (lenalidomide 10 mg), this will be deemed the Maximum Tolerated Dose (MTD). MTD is defined as the highest dose level at which < 33% of 6 patients experience a DLT.

[figure not shown]
If a DLT occurs in ≥ 2 of 3 patients or ≥ 2 of 6 patients treated on Dose Cohort A (lenalidomide 15mg), there will be a dose de-escalation to Dose Cohort Z (lenalidomide 10 mg).

[figure not shown]
If a DLT occurs in ≥ 2 of 3 patients or ≥ 2 of 6 patients treated on Dose Cohort B (lenalidomide 20 mg) or the preceding dose level will be declared the MTD if there were no more than 1 DLT in this previous cohort.

If a DLT occurs in ≥ 2 of 3 patients or ≥ 2 of 6 patients on Dose Cohort Z (lenalidomide 10mg), the trial will be discontinued and the expanded cohort will not be implemented.

Once the MTD has been determined, 15 additional patients with relapsed refractory HL will be treated in in the Phase II portion of this trial at the MTD.

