5.7 Subject Withdrawal/Discontinuation Criteria

Subjects may withdraw consent at any time for any reason or be dropped from the trial at the discretion of the investigator should any untoward effect occur. In addition, a subject may be withdrawn by the investigator or the Sponsor if enrollment into the trial is inappropriate, the trial plan is violated, or for administrative and/or other safety reasons. Specific details regarding discontinuation or withdrawal are provided in Section 7.1.4 – Other Procedures.

A subject must be discontinued from the trial for any of the following reasons:

- The subject or legal representative (such as a parent or legal guardian) withdraws consent.
- Confirmed radiographic disease progression

Note: For unconfirmed radiographic disease progression, please see Section 5.2.2

Note: A subject may be granted an exception to continue on treatment with confirmed radiographic progression if clinically stable or clinically improved, please see Section 7.1.2.7.1

- Unacceptable adverse experiences as described in Section 5.2.1.2
- Intercurrent illness that prevents further administration of treatment
- Investigator's decision to withdraw the subject
- The subject has a confirmed positive serum pregnancy test

- Noncompliance with trial treatment or procedure requirements
- The subject is lost to follow-up
- Completed 24 months of uninterrupted treatment with pembrolizumab.
- Administrative reasons

The End of Treatment and Follow-up visit procedures are listed in Section 6 (Protocol Flow Chart) and Section 7.1.5 (Visit Requirements). After the end of treatment, each subject will be followed for 30 days for adverse event monitoring (serious adverse events will be collected for 90 days after the end of treatment as described in Section 7.2.3.1). Subjects who discontinue for reasons other than progressive disease will have post-treatment follow-up for disease status until disease progression, initiating a non-study cancer treatment, withdrawing consent or becoming lost to follow-up. After documented disease progression each subject will be followed by telephone for overall survival until death, withdrawal of consent, or the end of the study, whichever occurs first.

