5.7.1 Discontinuation of Study Therapy after CR

Discontinuation of treatment may be considered for subjects who have attained a confirmed CR or after completion of 12 months of therapy.

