6.2.4.5 Second Course Phase (Retreatment Period)

Subjects who stop pembrolizumab with SD or better may be eligible for up to one year of additional pembrolizumab therapy if they progress after stopping study treatment. This retreatment is termed the Second Course Phase of this study and is only available if the study remains open and the subject meets the following conditions:

- **Either**
 - Stopped initial treatment with pembrolizumab after attaining an investigator-determined confirmed CR according to revised response criteria for lymphoid malignancies²⁴ and
 - Was treated for at least 24 weeks with pembrolizumab before discontinuing therapy
 - Received at least two treatments with pembrolizumab beyond the date when the initial CR was declared

OR

- Had SD, PR or CR and stopped pembrolizumab treatment after 24 months of study therapy for reasons other than disease progression or intolerability

AND

- Experienced an investigator-determined confirmed radiographic disease progression after stopping their initial treatment with pembrolizumab
- Did not receive any anti-cancer treatment since the last dose of pembrolizumab

Product: Pembrolizumab and Lenalidomide

Protocol/Amendment No.: Version 3.1 July 18th, 2017

- Has a performance status of 0 or 1 on the ECOG Performance Scale
- Demonstrates adequate organ function as detailed in Section 5.1.2
- Female subject of childbearing potential should have a negative serum or urine pregnancy test within 72 hours prior to receiving retreatment with study medication.
- Female subject of childbearing potential should be willing to use 2 methods of birth control or be surgically sterile, or abstain from heterosexual activity for the course of the study through 120 days after the last dose of study medication (Reference Section 5.7.2). Subjects of child bearing potential are those who have not been surgically sterilized or have been free from menses for > 1 year.
- Male subject should agree to use an adequate method of contraception starting with the first dose of study therapy through 120 days after the last dose of study therapy.
- Does not have a history or current evidence of any condition, therapy, or laboratory abnormality that might interfere with the subject's participation for the full duration of the trial or is not in the best interest of the subject to participate, in the opinion of the treating investigator.

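### Section 6.2.4.2 caps treatment at 12 months, while Sections 2.1, 5.7 and 7.1 set 24 months; followed as written, it halves maximum exposure and closes the second course to SD and PR patients

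*Combined protocol and SAP*

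**What the plan says.** The current text gives two different ceilings on treatment.

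- **Section 6.2.4.2 (Treatment Period):** "treatment will continue until disease progression or toxicity up to 12 months".
- **Section 2.1 (Trial Design):** both drugs are given "until disease progression or toxicity up to 24 months". Section 7.1, the Phase I SAP, has the same wording.
- **Section 5.7:** the list of reasons for which a subject must be discontinued includes "Completed 24 months of uninterrupted treatment with pembrolizumab". No 12-month stop is on the list.

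Three further places assume 24 months without setting the cap themselves.

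- **Section 1.0:** duration of participation is "Until disease progression or toxicity up to 2 years".
- **Section 6.2.3.2:** subjects who "complete 24 months of treatment with pembrolizumab may discontinue treatment with the option of restarting treatment" are described.
- **Section 6.2.4.5:** one route into the second course is for a patient who "Had SD, PR or CR and stopped pembrolizumab treatment after 24 months of study therapy".

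Section 5.7.1 is the only other place that mentions 12 months as a treatment duration: "Discontinuation of treatment may be considered for subjects who have attained a confirmed CR or after completion of 12 months of therapy". The Phase II SAP (Section 7.2) states no duration.

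**The concern.** Sections 2.1, 7.1 and 6.2.4.2 use almost the same sentence, with the same two stopping reasons and a ceiling that differs by a factor of two. Section 6.2.4.2 is titled Treatment Period, so it is a natural place for a site to look up how long to treat.

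A site that follows it would stop patients who have neither progressed nor had unacceptable toxicity at half the maximum that the design section intends. Patients stopped this way in SD or PR would also lose access to retreatment. The trial has several sites, so practice could differ between them. For patients still on treatment at 12 months, exposure would then depend on which section the site followed, and the descriptive PFS and duration-of-response summaries might as well.

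**Working it through.** No design calculation in the plan uses treatment duration, so there is no stated figure to reproduce. The check compares the texts and converts the two limits into cycles.

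**1. Which limit is intended?**

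| Section | Limit | Force |
|---|---|---|
| 6.2.4.2 | 12 months | cap |
| 2.1 and 7.1 | 24 months | cap, within the dose-escalation text |
| 5.7 | 24 months of pembrolizumab | mandatory stop, all subjects |
| 1.0 | 2 years | duration of participation, whole trial |
| 6.2.3.2 and 6.2.4.5 | 24 months | assumed by the restart provisions |
| 5.7.1 | 12 months, or confirmed CR | optional stop |

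Under a 12-month cap the 24-month provisions in Sections 5.7, 6.2.3.2 and 6.2.4.5 could never apply to an initial course. Section 5.7.1 does not rescue the cap. If treatment had to end at 12 months, there would be no decision left to consider at that point. The summary of changes in Section 11.4 records no reduction to 12 months. The intended limit is therefore 24 months.

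**2. Exposure.** Cycles are 21 days (Section 6.2.4.2).

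- 12 months: 365.25 / 21 = 17.4 cycles.
- 24 months: 730.5 / 21 = 34.8 cycles.
- Difference: 34.8 − 17.4 = 17.4 cycles, half the maximum.

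**3. Access to the second course (Section 6.2.4.5).** There are two routes.

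- *CR route.* The patient stopped after a confirmed CR, "Was treated for at least 24 weeks with pembrolizumab before discontinuing therapy", and had at least two pembrolizumab treatments after CR was declared. The minimum exposure is 24 × 7 / 21 = 8 cycles. This fits within 17.4 cycles, so the route stays open.
- *24-month route.* It is open to SD, PR or CR and needs about 34.8 cycles. That cannot be reached under a cap of 17.4. It is the only route for SD and PR.

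**4. Patients affected.** The documents do not give the proportion still on treatment at 12 months. Assume 20% to 60%.

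- Phase 2: 17 × 0.20 = 3.4 to 17 × 0.60 = 10.2, or about 3 to 10 patients.
- Whole trial: 26 × 0.20 = 5.2 to 29 × 0.60 = 17.4, or about 5 to 17 patients.

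**5. Primary analysis.** The binomial test of CR rate in 17 patients does not take treatment duration as an input. Twelve months still covers 365.25 / 84 = 4.3 imaging intervals of 12 weeks. Under Section 6.2.4.4, imaging also continues every 12 weeks after a stop for reasons other than progression.

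**The case against.** The contradiction itself is not in dispute. The case on the other side is that its consequences are smaller than they look.

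- **The second course is conditional.** It is offered only while the study remains open. Section 1.0 gives 18–24 months of enrollment and 36–48 months of trial duration. A patient enrolled at month 18 to 24 completes 24 months of treatment at month 42 to 48, and must then progress before closure. For late enrollees the 24-month route is nearly or fully shut under either reading. This stands, and it limits the loss. It does not remove it: a patient enrolled at the start reaches 24 months with 12 to 24 months of trial time left.
- **Section 5.7.1 can have the same effect.** An SD or PR patient who chooses to stop at 12 months also misses the 24-month route. That is true, but an optional stop is a different matter from a compulsory one.
- **The patient counts rest on an assumed rate.** They do. The whole-trial count is the weaker one, because it applies one rate to HL and NHL patients alike. The counts also suppose that every site follows Section 6.2.4.2 and that nobody stops early under Section 5.7.1. The finding does not depend on them.
- **The 24-month sentences in Sections 2.1 and 7.1 sit in dose-escalation text.** Also true, but Sections 5.7, 6.2.3.2 and 6.2.4.5 are not limited to Phase 1, and nothing assigns 12 months to Phase 2.
- **Section 6.2.4.2 is a single outlying sentence.** Sites may well follow the design section instead. This lowers the probability of harm but leaves an operative instruction that is wrong.

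**Conclusion.** The concern holds. Section 6.2.4.2 conflicts with the design section, the Phase I SAP and the mandatory discontinuation list, and no other provision reconciles them. Followed as written, it halves maximum treatment and makes retreatment unreachable for SD and PR patients. These two results follow from the text and need no assumption beyond calendar arithmetic. The number of patients affected is not known; 3 to 10 of 17 in Phase 2 is illustrative only. The sample size, alpha and power of the CR test are untouched, and any effect on PFS and duration of response concerns descriptive summaries. The error should be corrected because it governs how long patients are treated, although it does not threaten the primary test.

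**What to change.** In Section 6.2.4.2, replace 12 months with 24 months, so that it agrees with Sections 2.1, 5.7 and 7.1. Keep Section 5.7.1 as an explicitly optional earlier stop after confirmed CR or 12 months.

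The cost is one phrase in an amendment. Sample size, alpha, power and visit schedule do not change.

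A separate mismatch could be tidied in the same amendment: Section 5.7 requires a stop at 24 months of pembrolizumab, whereas Section 6.2.3.2 words it as optional. Resolving this conflict does not depend on that.

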6.2.4.3 Post-Treatment Visits

7.1.5.3.1 Safety Follow-Up Visit

The mandatory Safety Follow-Up Visit should be conducted approximately 30 days after the last dose of trial treatment or before the initiation of a new anti-cancer treatment, whichever comes first. All AEs that occur prior to the Safety Follow-Up Visit should be recorded. Subjects with an AE of Grade > 1 will be followed until the resolution of the AE to Grade 0-1 or until the beginning of a new anti-neoplastic therapy, whichever occurs first. SAEs that occur within 90 days of the end of treatment or before initiation of a new anti-cancer treatment should also be followed and recorded. Subjects who are eligible for retreatment with pembrolizumab (as described in Section 7.1.5.5) may have up to two safety follow-up visits, one after the Treatment Period and one after the Second Course Phase.

6.2.4.4 Follow-up Visits

Subjects who discontinue trial treatment for a reason other than disease progression will move into the Follow-Up Phase and tumor imaging will occur every 12 weeks (\pm 7 days). Every effort should be made to collect information regarding disease status until the start of new anti-neoplastic therapy, disease progression, death, end of the study or if the subject begins retreatment with pembrolizumab as detailed in Section 7.1.5.5. Information regarding post-study anti-neoplastic treatment will be collected if new treatment is initiated.

Product: Pembrolizumab and Lenalidomide
Protocol/Amendment No.: Version 3.1 July 18th, 2017

Subjects who are eligible to receive retreatment with pembrolizumab according to the criteria in Section 7.1.5.5 will move from the follow-up phase to the Second Course Phase when they experience disease progression.

6.2.4.4.1 Survival Follow-up

Once a subject experiences confirmed disease progression or starts a new anti-cancer therapy, the subject moves into the survival follow-up phase and should be contacted by telephone every 12 weeks to assess for survival status until death, withdrawal of consent, or the end of the study, whichever occurs first.

6.2.4.5 Second Course Phase (Retreatment Period)

Subjects who stop pembrolizumab with SD or better may be eligible for up to one year of additional pembrolizumab therapy if they progress after stopping study treatment. This retreatment is termed the Second Course Phase of this study and is only available if the study remains open and the subject meets the following conditions:

- **Either**
 - Stopped initial treatment with pembrolizumab after attaining an investigator-determined confirmed CR according to revised response criteria for lymphoid malignancies²⁴ and
 - Was treated for at least 24 weeks with pembrolizumab before discontinuing therapy
 - Received at least two treatments with pembrolizumab beyond the date when the initial CR was declared

OR

- Had SD, PR or CR and stopped pembrolizumab treatment after 24 months of study therapy for reasons other than disease progression or intolerability

AND

- Experienced an investigator-determined confirmed radiographic disease progression after stopping their initial treatment with pembrolizumab
- Did not receive any anti-cancer treatment since the last dose of pembrolizumab

Product: Pembrolizumab and Lenalidomide

Protocol/Amendment No.: Version 3.1 July 18th, 2017

- Has a performance status of 0 or 1 on the ECOG Performance Scale
- Demonstrates adequate organ function as detailed in Section 5.1.2
- Female subject of childbearing potential should have a negative serum or urine pregnancy test within 72 hours prior to receiving retreatment with study medication.
- Female subject of childbearing potential should be willing to use 2 methods of birth control or be surgically sterile, or abstain from heterosexual activity for the course of the study through 120 days after the last dose of study medication (Reference Section 5.7.2). Subjects of child bearing potential are those who have not been surgically sterilized or have been free from menses for > 1 year.
- Male subject should agree to use an adequate method of contraception starting with the first dose of study therapy through 120 days after the last dose of study therapy.
- Does not have a history or current evidence of any condition, therapy, or laboratory abnormality that might interfere with the subject's participation for the full duration of the trial or is not in the best interest of the subject to participate, in the opinion of the treating investigator.

Subjects who restart treatment will be retreated at the same dose and dose interval as when they last received pembrolizumab. Treatment will be administered for up to one additional year.

Visit requirements are outlined in Section 6.0 – Trial Flow Chart.

